9.2 LABORATORY ASSESSMENTS

Refer to CSPM for detailed instructions for all sample handling.

The acceptable deviations from the nominal blood sampling time points for biochemistry, hematology, serology and coagulation are:

- The pre-dose blood sample will be taken up to 2 hours before dosing
- 2 to 12 hour post-dose blood samples will be taken within ± 10 minutes of the nominal post-dose sampling time
- 24 to 120 hour post-dose blood samples will be taken within ± 30 minutes of the nominal post-dose sampling time

The acceptable deviations from the nominal urine sampling time points for urinalysis are:

- The pre-dose urine sample will be taken from the 24 hour (day-1) urine collection within 1 hour of nominal timepoint).
- Post-dose urine samples will be taken ± 1 hour from the nominal urine sampling time

The acceptable deviations for PK blood and bioanalytical urine samples can be found in Section 9.2.6.

In cases where laboratory findings are outside the normal range and the investigator believes that the results may be of clinical significance, repeat sampling may be requested as clinically indicated. If the abnormal finding is clinically significant, appropriate actions will be taken e.g., the subject will not be entered into the study, or the subject may be withdrawn from the study. The subject will be referred to their primary care provider or other appropriate provider for further care if necessary. The same will apply if the results of the HBsAg, HCV Ab, or HIV test are positive and in addition the investigator will ensure that adequate counselling is available if requested.

Abnormal results at follow-up assessments will also require repeat testing if the investigator believes the results may be of clinical significance.

Any clinically significant abnormality, including changes from baseline, must be reported as an AE.

Additional blood and/or urine samples may be taken for safety tests. Furthermore, additional assays outside those specified in the protocol may be performed for safety reasons as requested by the investigator.

9.2.1 BIOCHEMISTRY

Biochemistry will be performed at the time points specified in Section 3.2 (SoA). The following will be assessed: Alanine Aminotransferase (ALT), Albumin, Alkaline Phosphatase, Aspartate Aminotransferase (AST), Bilirubin (Total), Bilirubin (Direct), BUN, Calcium, Carbon Dioxide, Chloride, Creatine Kinase (CK), serum Creatinine, eGFR will be calculated at screening using CKP-EPI 2021 Refit equation for eligibility

purposes, Follicle Stimulating Hormone (FSH; post-menopausal female subjects only when indicated), Glucose (unscheduled time points), Glucose (Fasting), Human Chorionic Gonadotropin (hCG) (female subjects when indicated), Potassium, Phosphate (Inorganic), Protein (Total), Sodium, and Lipid profile (cholesterol, HDL, LDL, triglycerides).

9.2.2 SEROLOGY

Hepatitis B (HBsAg) antigen, HCV antibody, and HIV antibody detection will be performed at screening.

9.2.3 HEMATOLOGY

Hematology will be performed at screening, on admission, approximately at 24 hours post-dose, and before discharge. The following will be assessed: Basophils, Eosinophils, Hematocrit, Hemoglobin, Lymphocytes, Mean Cell Hemoglobin, Mean Cell Hemoglobin Concentration, Mean Cell Volume, Monocytes, Neutrophils, Platelet Count, RBC Count, Red Cell Distribution Width, Mean Platelet Volume, and WBC Count.

9.2.4 COAGULATION

Pt, INR, and APTT will be performed at screening, on admission, and approximately at 24 hours post-dose.

9.2.5 URINALYSIS

Urinalysis will be performed at screening, and on admission. Small spot urine sample collections for urinalysis will be collected at the end of each 24 hour urine collection interval for elimination studies. The following will be assessed: pH, specific gravity, protein, glucose, ketones, bilirubin, blood, nitrite, urobilinogen, and leukocytes. Unless otherwise specified, microscopic examination will be performed on abnormal findings.

In addition, an aliquot of urine from each 24 hour collection will be analyzed for 24 hour urine creatinine

. The 24 hour urine creatinine, 24 hour urine volume, and corresponding serum creatinine will be used to calculate 24 hour urine creatinine clearance.

9.2.6 BIOANALYTICAL SAMPLE COLLECTION AND PROCESSING

Plasma and urine will be analyzed by high performance LC-MS/MS to measure the concentration of intact RVP-001 in order to assess plasma pharmacokinetics at Inotiv. Separate urine and feces samples will be analyzed by ICP-MS for total Mn content to quantify elimination of injected Mn and fractional excretion at Quotient Bioanalytical. Separate plasma and urine samples will be sent to Massachusetts General Hospital for exploratory studies.

A total of 16 blood samples will be drawn from each subject for PK analyses. Venous blood will be collected prior to (within 2 hours prior to dose) and at 2, 5, 10, 20, and 30 minutes after the end of the bolus dose and at 1, 2, 4, 8, 12, 24, 48, 72, 96, and 120 hours post-dose (6 mL for each sampling time).

The acceptable deviations from the nominal blood sampling times are as follows:

- The pre-dose samples will be taken up to 2 hours before dosing
- 0 to 1 hour post-dose samples will be taken within ± 2 minutes of the nominal post-dose sampling time
- 2 to 12 hour post-dose samples will be taken within ± 10 minutes of the nominal post-dose sampling time
- 24 to 120 hour post-dose samples will be taken within ± 30 minutes of the nominal postdose sampling time

The total blood volume withdrawn from each subject will not exceed 550 mL in an 8 week period (based on a representative healthy subject weighing at least 110 pounds). The blood volume taken during the study is presented in Table 5. The number and timing of samples may be amended following any interim PK parameter estimations.

Version 2.0: 9 May 2022 Confidential Page 54

[figure not shown]
Table 5 Estimated Total Blood Volume

| Study Visit | Sample Type | Number of Samples | Sample Volume | Total Volume |
|---------------------------|----------------------------------------------------------------------------------------------------|----------------------|---------------------|--------------|
| Screening | Safety laboratory assessments (biochemistry [including FSH], hematology, coagulation and serology) | 1 | 22.7 mL | 22.7 mL |
| Admission (Day -1) | Safety laboratory assessments (biochemistry [including pregnancy], hematology, and coagulation) | 1 | 15.2 mL | 15.2 mL |
| Day 1 | Safety laboratory assessments (biochemistry, hematology, and coagulation) | 2 | 14.2 mL | 28.4 mL |
| Day 1 to Day 6 | Pharmacokinetic assessments | 16 | 6.0 mL | 96.0 mL |
| Day 2 to Day 6 | Safety laboratory assessments (biochemistry, hematology, and coagulation) | 5 | 14.2 mL | 71.0 mL |
| FCII fellisle discolution | | ood Volume per S | Subject per Cohort: | 233.3 mL |

FSH = follicle stimulating hormone

Actual sampling times will be used for statistical analyses. Blood samples will be collected by direct venipuncture as per clinical site operational practice.

Deviations of blood volume will be reported only when the total volume of the whole study is exceeded.

The acceptable deviations from the nominal urine sampling times are as follows:

 The -24 hours to 0 hours urine collection will be collected within -180 minutes to +60 minutes of the nominal dose sampling time

 The subsequent 24 hour urine collections will be collected within ± 60 minutes of the nominal post-dose sampling time

Urine samples will be collected as individual samples and combined in the following time intervals: -24-0 hours, 0-24 hours, 24-48 hours, 48-72 hours, 72-96 hours, 96-120 hours. Each sample will be weighed prior to combining. After final collection for each container, total sample will be weighed, and urine volume measured. Aliquots will be removed for urinalysis and additional aliquots will be sent for following analyses: (i) Elimination evaluation RVP-001: ship to (ii) Elimination evaluation total Mn: ship to (iii) Developmental Analysis: (iv) Banking: Stored at -80 °C at per GLP standards.

Feces samples will be collected in the following intervals: -24-0 hours, 0-24 hours, 24-48 hours, 48-72 hours, 72-96 hours, 96-120 hours. Individual samples will be collected, labeled, and stored. Samples will be prepared as per the agreed upon procedures of the bioanalytical laboratory and CSPM, and then shipped to

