|---------------------------------------------|-----------|-----------|------|----|---|---|---|------|-------------------------------------------|-----------------------------------|
| Day | -28 to -2 | -1 | 1 | 2 | 3 | 4 | 5 | 61,2 | 8 ³ | 9-304 |
| Alcohol, cotinine and drugs of abuse screen | X | Х | | | Т | Г | Ī | | ĺ | |
| Pregnancy test ¹⁷ | X | Х | | | Τ | Τ | T | Х | | |
| FSH ¹⁸ | х | | | | T | T | T | T | | |
| RVP-001 administration | | | х | K. | T | T | | 1581 | | 1 |
| Injection site monitoring ¹⁹ | | | Х | Х | х | х | х | Х | | |
| Blood PK samples ²⁰ | * | | Х | Х | х | х | х | х | | |
| 7 SM SM I | | х | X | x | х | х | х | X | | |
| Urine and Feces samples ^{21, 22} | | | | | | | | | | f |

AE = adverse event

¹⁷ A highly sensitive urine pregnancy test will be performed at screening for all female subjects. For women of childbearing potential, a highly sensitive urine pregnancy test will also be performed before discharge. A highly sensitive serum pregnancy test will be performed at admission.

¹⁸ Post-menopausal females only.

¹⁹ Injection site monitoring daily until discharge.

²⁰ Blood samples for PK assessment will be collected prior (within 2 hours prior to dose) and at 2, 5, 10, 20, and 30 minutes after the end of the bolus dose and at 1, 2, 4, 8, 12, 24, 48, 72, 96, and 120 hours post-dose (6 mL for each sampling time).

²¹ All urine and feces will be collected for PK and elimination studies and be retained in 24-hour bins. Urine samples will be collected in the following approximate time intervals: -24-0 hours, 0-24 hours, 24-48 hours, 48-72 hours, 72-96 hours, 96-120 hours. Feces samples (entire stool) will be collected in the following approximate time intervals: -24-0 hours, 0-24 hours, 24-48 hours, 48-72 hours, 72-96 hours, 96-120 hours.

²² Pre-dose 24 hour urine collection may be less than 24 hrs depending on time subject enters CSU to time of dosing.

| Assessment | Screening -28 to -2 | Admission | | | Da | ys | | | Post-Treatment Phase Follow-up Phone Call | Subjects to Self-report AEs 9-30 ⁴ |
|----------------------------------|------------------------|-----------|---|---|----|----|---|------|-------------------------------------------|--------------------------------------------------------|
| Day | | -1 | 1 | 2 | 3 | 4 | 5 | 61,2 | 8 ³ | |
| Fluid Monitoring ²³ | | Х | Х | Х | х | х | х | х | | |
| Discharge from clinical site | | | | | T | Г | Г | х | | |

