7.1.2 ADMINISTRATION OF STUDY DRUG, MEALS, AND FLUIDS

All injectables will be prepared in the laboratory and administered using amber tinted syringes and IV tubing. Power injectors will be used to standardize injection times of the bolus and the saline flush that follows. Specific details of study drug and doses to be administered are provided in Section 7.2.3 and Section 5.2, respectively. Subjects will be dosed on the morning of Day 1.

The exact time of dosing will be decided based on logistics and will be documented in Electronic Case Report Forms (eCRF). Details of the procedures adopted for maintaining the study blind during dosing are provided in Section 7.3. If appearance matching of the placebo is not possible then masking and/or unblinded dosing teams will be used to preserve the study blind. Further details of these steps will be contained in the study specific blinding plan, which will be approved prior to dosing (see also Section 7.3). For each subject, all scheduled post dose activities and assessments will be performed relative to the time of study drug administration (see Section 9.5 for further details). Reference time for all post-dose activities will be time of beginning of bolus dose injection.

A staggered dosing schedule will be used. In each cohort 2 sentinel subjects (1 active and 1 placebo) will be dosed first and the remaining 6 subjects (5 active and 1 placebo) will be dosed 24 hours later. All cohorts will be dosed in a similar manner. See Section 7.3 for further details.

To assess tolerability of the IV administration, the first subject will be dosed at least 30 min prior to dosing the second subject. All subsequent dosing of the study drug will be staggered by at least 15 min. To allow

for potential interruptions and injector variations, up to a 20% difference in duration of the infusion will not be considered as a protocol deviation provided that full planned dose is administered. Any such minor discrepancies should not have a significant impact on the overall study objectives.

The planned injection time will be approximately 5-15 sec (depending upon patient weight/dose); the actual infusion start and stop time will be recorded in the source documents. In all cases, the study drug injection will be followed by 20 second injection of normal saline.

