9.1.2 VITAL SIGNS

BP, respiratory rate, HR, and body temperature will be measured in a supine position (except for safety reasons) at the time points described in Section 3.2 (SOA). HR and pulse oximetry will be monitored continuously for 4 hours post dose.

Subject should be in supine position at least 5 minutes prior to measurements.

The acceptable deviations from the nominal vital signs measurement time points are:

- The pre-dose vital signs measurements will be taken ≤2 h before dosing.
- Post-dose vital signs measurements will be taken ± 2 min from the nominal post-dose time points for the first hour. Post-dose vital signs measurements will be taken ± 15 min from all other nominal post-dose time points.
- Discharge vital signs measurements will be taken ± 1 h from the nominal time point.

If a subject shows an abnormal assessment at any stage, repeat measurements may be made and the abnormality followed to resolution if required. Additional measurements may be taken as deemed necessary by the investigator or sub-investigator.

Any clinically significant abnormality, including changes from baseline, must be reported as an AE.

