9.1.3 ECG MEASUREMENTS

Supine (single) 12-lead ECGs will be taken at 1, 3 and 8 minutes post dose after the subject has been in the supine position for a minimum of 5 min. Supine triplicate 12-lead ECGs (3 ECGs taken approximately 1 minute apart) after the subject has been in the supine position for a minimum of 5 min will be performed at the nominal timepoints in Section 3.2 (SoA). For triplicate ECGs, the mean of the three recordings will be reported.

- The pre-dose ECG measurements will be taken ≤2 h before dosing
- Post-dose single ECG measurements (minutes 1, 3 and 8) will be taken ± 2 min from the nominal post-dose time point
- All other ECGs will be taken ± 10 min for first 3 hours (excluding above) post dose and ± 30 min thereafter.
- Discharge ECG measurements will be taken ± 1 h from the nominal time point.

If a subject shows an abnormal assessment at any stage, repeat measurements may be made and the abnormality followed to resolution if required. Additional measurements may be taken as deemed necessary by the investigator or sub-investigator.

Any clinically significant abnormality, including changes from baseline, will be reported as an AE.

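### The tolerance on the -24 to 0 h urine runs 60 minutes past an undefined nominal time, so a post-dose void can enter the pre-dose bin without being a deviation

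*Combined protocol and SAP*

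**What the plan says.** Protocol section 9.2.6 lists acceptable deviations for urine. For the -24 to 0 h interval it allows that the "urine collection will be collected within -180 minutes to +60 minutes of the nominal dose sampling time". That nominal time appears only in this sentence and is tied to nothing else. The later 24-hour collections have a tolerance of 60 minutes either way.

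The same section sets the bins: "Urine samples will be collected as individual samples and combined in the following time intervals", the first two being -24 to 0 h and 0 to 24 h. Section 7.1.2 fixes time zero: "Reference time for all post-dose activities will be time of beginning of bolus dose injection". It leaves the clock time of dosing to logistics. Schedule of Activities footnote 22 adds: "Pre-dose 24 hour urine collection may be less than 24 hrs depending on time subject enters CSU to time of dosing".

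Section 9.2 takes the pre-dose urinalysis sample from this same collection, with a one-hour tolerance around a time point that it also leaves unspecified.

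The urine is assayed for intact RVP-001 and for total manganese (9.2.6). Elimination is part of the secondary objective (4.4), and section 10.2.8 summarises urinary RVP-001 by collection interval.

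**The concern.** The boundary at hour 0 separates urine that cannot contain the drug from urine that does. If the tolerance reaches past injection, a void containing RVP-001 can be pooled into the bin labelled pre-dose and nobody need record a deviation. Once voids are pooled, actual sampling times cannot separate them.

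In an affected subject the 0-24 h amounts of RVP-001 and manganese would be too low, and the pre-dose bin would contain injected material. Cumulative recovery would be understated only if the pre-dose bin is left out of the sum.

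The reach is limited. Cmax and AUC do not use urine, and adverse events, ECGs, vital signs and blood laboratory tests are untouched. Among the safety data, only the pre-dose urinalysis sample and the 24-hour creatinine clearance (9.2.5) draw on the same collections.

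**Working it through.** The plan gives no figure to reproduce. The check compares the passages and then sizes the effect under stated assumptions.

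**1. How much of the window lies after dosing.** The window is 180 + 60 = 240 minutes wide. If the actual dose is d minutes after the nominal time, the accepted post-dose span is max(0, 60 - d).

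| Actual dose relative to nominal time | Accepted post-dose span |
|---|---|
| 30 min early | 90 min |
| on time | 60 min (60/240 = 25% of the window) |
| 30 min late | 30 min |
| 60 min late or more | 0 min |

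With on-time dosing, a void at 30 minutes is therefore acceptable in the -24 to 0 h collection and also belongs to the 0 to 24 h bin by definition. No supplied section requires a void before dosing or closes the bin at injection.

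**2. Size in an affected subject.** Section 6.5 says that the human half-life is unknown, so the half-lives below are assumptions. The model is first-order elimination with full bladder emptying and one misplaced void at h hours. The urinary amount up to time h is (urinary fraction) × (dose) × (1 - 2^(-h/t½)). As a share of the 0-24 h amount, the urinary fraction and the dose cancel:

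share = (1 - 2^(-h/t½)) / (1 - 2^(-24/t½))

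Example, t½ = 6 h and h = 1: (1 - 0.8909) / (1 - 0.0625) = 0.1091 / 0.9375 = 11.6%.

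| Assumed t½ | Void at 15 min | Void at 30 min | Void at 60 min |
|---|---|---|---|
| 1 h | 15.9% | 29.3% | 50.0% |
| 3 h | 5.6% | 11.0% | 20.7% |
| 6 h | 3.0% | 6.0% | 11.6% |

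The 60-minute column is the upper bound for on-time dosing. Incomplete emptying reduces every entry, and the effect is zero if there is no void in the window. Outside the assumed range, the 60-minute share would be 75% at a half-life of 0.5 h and 9.5% at 8 h.

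**3. Size in a cohort mean.** With one affected subject among six on active drug and equal true recoveries, the mean 0-24 h recovery falls by share/6.

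| Assumed t½ | 15 min | 30 min | 60 min |
|---|---|---|---|
| 1 h | 2.7% | 4.9% | 8.3% |
| 3 h | 0.9% | 1.8% | 3.5% |
| 6 h | 0.5% | 1.0% | 1.9% |

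**4. Why an hour matters here and not at later boundaries.** At an assumed half-life of 3 h, 1 - 2^(-1/3) = 20.6% of the eventual urinary amount is excreted in hour 0-1. Hour 24-25 carries 2^(-8) × 20.6% = 0.08%. The same tolerance is nearly harmless at 24 h and beyond.

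**The case against.** The strongest reply is that the bin rule already decides the matter. Voids are collected individually, time zero is the start of the bolus, and footnote 22 calls the first collection pre-dose, so a void after injection is a 0-24 h sample whatever the timing tolerance says. This stands in part: the intended cut-off is visible. But the tolerance is a stated rule that accepts collection past that cut-off, and no text says which prevails.

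Two other readings would shrink or remove the problem. The +60 minutes may be meant for late dosing, or the window may apply to the start of the collection, since arrival is only approximately 24 hours before dosing. Both are possible; the words compel neither.

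The sample processing manual, to which section 9.2 refers for all sample handling, and the separate SAP are not supplied and may contain a rule. That is a reason to check them.

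Likelihood is low. The first hour has ECGs, supine vital signs, PK draws and continuous heart-rate and oximetry monitoring, and no water is scheduled from one hour before dosing until one hour after. The documents give no basis for a probability. Detection is also likely, because intact RVP-001 is assayed in urine and can come only from the dose. Both points stand and limit the weight of the concern.

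The pre-dose windows for other measurements end at dosing, for example "The pre-dose ECG measurements will be taken ≤2 h before dosing" for ECGs and "The pre-dose samples will be taken up to 2 hours before dosing" for PK blood. These govern point measurements, so they are analogies to an interval collection and not contradictions of it.

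**Conclusion.** The point holds as an internal inconsistency of modest consequence. Section 9.2.6 tolerates a post-dose void in the pre-dose bin if the nominal time is the subject's dosing time and dosing is on schedule. Under assumed half-lives of 1-6 h and full emptying, an affected subject loses about 3-16% (void at 15 minutes) to about 12-50% (void at 60 minutes, upper bound) of 0-24 h urinary recovery. One affected subject of six moves the cohort mean by about 0.5-2.7% or 1.9-8.3%.

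Three stronger inferences are not supported:

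- A reader might infer that the protocol directs post-dose urine into the pre-dose bin. It permits this and does not direct it.
- A reader might infer a biased baseline-corrected manganese recovery. The supplied text never says that pre-dose manganese is subtracted.
- A reader might count how many subjects in a cohort are exposed if one clock time serves the whole group. If it is set at the first main-group dose, the minimum 15-minute stagger leaves spans of 60, 45, 30, 15, 0 and 0 minutes, so four of six. A 30-minute stagger leaves 60, 30, 0, 0, 0 and 0, so two of six. One of the six is on placebo. The count depends on a nominal time and a stagger that the documents do not fix.

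**What to change.** In section 9.2.6, end the -24 to 0 h bin at the last void before the actual start of injection, with no positive tolerance. Assign every later void to 0-24 h and record the actual start and stop time of each bin. Apply the same cut-off to the pre-dose urinalysis sample in section 9.2. Define the nominal time or delete it, and confirm that the sample processing manual agrees.

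The accepted post-dose span then falls from as much as 60 minutes with on-time dosing to zero. The cost is one line in 9.2.6, a matching line in 9.2 and an entry in the collection log, with no extra samples, visits or subjects. The downside is that some pre-dose bins will be shorter than 24 hours, which footnote 22 already accepts.
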